# Protocol Details

## Basic Info

Confirmation Number:	eaicdefj
Protocol Number:	855282
Created By:	[name]
Principal Investigator:	[name]
Protocol Title:	A Randomized Controlled Trial of a Wellness App for First Responders, Military Personnel and Veterans
Short Title:	The GUIDE App RCT
Protocol Description:	The purpose of the research study is to trial a smart phone application, the GUIDE App, to better understand its impact on social connectedness, personal growth and mental health/wellness among first responders, soldiers, and veterans. The research team will also investigate workplace metrics (e.g., engagement and burnout), implementation outcomes and technical merit. We plan to run a three-armed randomized waitlist pilot feasibility trial with up to 150 participants.
Submission Type:	Social and Biological Sciences
Application Type:	FULL

## Resubmission\*

Yes

## Hospital Sites

Will any research activities and/or services be conducted at a Penn Medicine affiliated hospital site?

No

## **Other Investigator**

None

## **Responsible Org (Department/School/Division):**

4412 - PS-Psychiatry

## **Penn Intellectual Property\***

To the best of the Principal Investigator's knowledge, does this protocol involve the testing, development or evaluation of a drug, device, product, or other type of intellectual property (IP) that is owned by or assigned to the University of Pennsylvania? Please refer to the Patent and Tangible Research Property Policies and Procedures.

No

## **Certification**

I have reviewed the *Financial Disclosure and Presumptively Prohibited Conflicts for Faculty Participating in Clinical Trials* and the *Financial Disclosure Policy for Research and Sponsored Projects* with all persons who are responsible for the design, conduct, or reporting of this research; and all required Disclosures have been attached to this application.

Yes

# Social and Biological Sciences

## Study Instruments

Discuss the particulars of the research instruments, questionnaires and other evaluation instruments in detail. Provide validation documentation and or procedures to be used to validate instruments. For well known and generally accepted test instruments the detail here can be brief. More detail may be required for a novel or new instrument. For ethnographic studies identify any study instruments to be used (i.e. for deception studies) and describe in detail where, when and how the study will be conducted and who or what are the subjects of study. Note: For more information on how to conduct ethical and valid ethnographic research, follow the link For oral histories or interviews provide the general framework for questioning and means of data collection. If interviews or groups settings are to be audio taped or video taped describe in detail the conditions under which it will take place. Include a copy of any novel or new test instruments with the IRB submission.

The purpose of this study is to measure how the GUIDE App impacts social connectedness, personal growth, mental health/wellness, workplace engagement and burnout, among first responders, soldiers, and veterans. Participants assigned to the immediate and immediate with incentives groups will use the GUIDE App for their 4-week trial period. Participants in the waitlist group will be offered access at the end of the trial. The GUIDE App is a wellbeing app designed with first responders and veterans in mind. Because there is a stigma associated with seeking help and getting connected with resources, the GUIDE mobile app uses small group support, a learning management system, drivers of behavior change, and an anonymous member experience safeguarded by a leader in identity and login privacy, Okta (okta.com). It includes three main features: 1) Community, 2) Wisdom, and 3) Daily Practice. The Community feature connects app users with an online community of like folks, allowing for human support, encouragement, accountability and coaching. Online communities are moderated by GUIDE employees. The Wisdom feature includes tools and interactive media for personal growth. The Daily Practice feature includes simple, daily routines to maintain mental and emotional wellness. While using the app, participants will be given the opportunity to complete assessments that screen for depression (PHQ-9), PTSD (PC-PTSD-5), insomnia (ICD-10), anxiety (GAD-7), alcoholism (AUDIT), and suicide (ASQ) in their Courses. Before the assessment is administered, participants must watch a 2-minute video about the selected measure and its effectiveness, why it is used and by whom, and how it is a screener (i.e., not a diagnostic tool) that should be used to determine whether further testing or treatment should be solicited. Scores from these measures are not tabulated or collected by GUIDE. When participants finish filling out the assessment, they are brought to a screen that shows them how to score their own responses. The SOS button on the app is highlighted for the first several seconds to remind them that there are resources available. The following crises numbers are built into the SOS button: Suicide and Crisis Lifeline, Veteran Crisis Line, Substance Abuse and Mental Health Services Administration, Disaster Distress Hotline, Red Nacional de Prevencion del Suicido, COPLINE, Firefights Union for PTSD & Mental Health, Frontline Helpline, Fire/EMS Helpline, Safe Call Now, and the All Clear Foundation. The research team will use baseline and post-trial assessments, administered via REDCap survey, to measure how app access impacts the primary and secondary proximal outcomes, as well as secondary distal outcomes, as proposed by our Theory of Change Model (attached), e.g., that by engaging with the GUIDE App, first responders/soldiers/veterans who commonly feel isolated, seek opportunities for personal growth, and have mental health challenges will build resilience using the Community, Wisdom, and Daily Practice features, influencing the primary proximal outcome of mental health/wellness, as well as the secondary proximal outcomes of social connectedness and personal growth. We propose that these proximal outcomes will then positively influence the secondary distal outcomes, including worker engagement and burnout. To measure App Engagement, we will use app metrics collected by GUIDE, including lessons completed, courses completed, small group posts, small group comments, journal entries, wellness check-ins, and usage streaks. To measure Mental Health/Wellbeing, we rely on a number of well-known and robust instruments including: the Patient Health Questionnaire for depression symptoms (PHQ-8); the Generalized Anxiety Disorder-7 (GAD-7), the 5-Item World Health Organization Well-Being Index (WHO-5), the Difficulties in Emotion Regulation Scale Short Form (DERS-SF), the overall score and Positive Emotion sub-scale from the PERMA-Profilier, and the Personal Wellbeing Score (PWS). To measure Social Connectedness, we will use the Engagement and Relationships sub-scales from the PERMA-profilier. We will also use metrics collected by GUIDE, including the number of comments and

posts the participant creates in the app (1st vs. last week). To measure Personal Growth, we will use the Meaning and Accomplishment sub-scales from the PERMA-Profiler. We will also use metrics collected by GUIDE, including the number of lessons/courses completed. To measure Workplace Engagement, we will use Utrecht Work Engagement Scale (UWES) and the Maslach Burnout Inventory (MBI), both highly reliable and well-established measures in use for decades. In addition to the above measures, we will also be asking participants to answer questions about the app in the post-trial assessment survey. To measure Implementation and Technical Merit of the app, we will use the Feasibility of Intervention Measure (FIM), the Acceptability of Intervention Measure (AIM), the Intervention Appropriateness Measure (IAM) and the System Usability Scale (SUS). During the post-trial meeting, we will review a brief Adverse Event Checklist with participants. This checklist contains four questions and is attached to this application.

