During GUIDE account creation, participants will be required to provide their phone number and/or email address. This personal data will be secured by Okta, a third-party authentication provider, and stored separately from app data. Screenshots of this process can be found in the GUIDE Account Creation document attached to this application. When the meeting is over, all participants will receive an email from the research team with a link to a calendar management software, such as Microsoft Bookings, requesting that they schedule their post-trial meeting for 4-5 weeks out from the intake meeting. During the trial period of 4 weeks, participants in the immediate and immediate with incentives groups will have full access to the GUIDE App. To get started, the app will prompt participants to answer a series of onboarding questions about themselves, including their goals, wellness experience and demographic information (see attached GUIDE Onboarding Process). Based on their responses, participants will be assigned Courses and Daily Practices; as well as a personalized small group chat, where they can post and comment with likeminded others, anonymously, with the option to share app progress. Courses are composed of lessons, and include topics like Forgiveness, Gratitude, and Self-Awareness. The lessons contain a mix of media including videos, assessments, readings and exercises. Courses and lessons take varying amounts of time to complete, which the participant can see before adding it to their profile. The app also includes three types of Daily Practices including Meditation Practice (a simple timer to help keep participants focused while they meditate), Journal Practice (where participants can catalog their thoughts and reactions to lessons), and a Mood Tracker that participants can view over time (How are you feeling? 1 = Very Sad to 5 = Very Happy). On the home page, participants are invited to track their Wellness Score, based on the Personal Wellbeing Score (PWS), over time to see trends. Screenshots of GUIDE app content, and information about how it works, can be found in the GUIDE App Content document attached. The GUIDE App invites participants to complete assessments that screen for PTSD (PC-PTSD-5), insomnia (ICD-10), anxiety (GAD-7), and alcoholism (AUDIT) in their Courses. Before the assessment is administered, participants must watch a 2-minute video about the selected measure and its effectiveness, why it is used and by whom, and how it is a screener (i.e., not a diagnostic tool) that should be used to determine whether further testing or treatment should be solicited. Scores from these measures are not tabulated or collected by GUIDE. When participants finish filling out the assessment, they are brought to a screen that shows them how to score their own responses. For people needing a higher level of care, the following crises numbers are provided in the app: Suicide and Crisis Lifeline, Veteran Crisis Line, Substance Abuse and Mental Health Services Administration, Disaster Distress Hotline, Red Nacional de Prevencion del Suicido, COPLINE, Firefights Union for PTSD & Mental Health, Frontline Helpline, Fire/EMS Helpline, Safe Call Now, and the All Clear Foundation. Participants assigned to the immediate with incentives group will be asked to complete certain weekly tasks in the app order to receive an Amazon gift card for their participation. Required tasks include visiting the GUIDE App at least four times, completing at least one lesson, posting at least one time, commenting at least one time, and completing at least one wellness check-in. When the four-week trial period is over, participants will receive an email from REDCap with a link to their post-trial assessment survey. The survey for participants in the waitlist will contain 100 questions and take about 20 minutes to complete. The survey for participants in the immediate and immediate with incentives groups will contain 123 questions, including questions about app implementation and technical merit, and will take approximately 20-30 minutes to complete. Participants who have not yet scheduled their post-trial meeting will receive an additional email reminder from the research team, along with a link to a calendar management software, such as Microsoft Bookings. During the post-trial Zoom meeting, participants who have not yet completed their post-trial assessment will be given time to do so. They will get the opportunity to give feedback about the GUIDE App and the trial. The meeting will be brief, about 15 minutes, and will not be recorded. Participants will receive \$50 in compensation for completing this survey, remitted through a Greenphire ClinCard®. The research team will also review a brief Adverse Event Checklist with these participants and record their responses. This checklist contains four questions and is attached to this application. Participants in the immediate and immediate with incentives groups will be told they may delete their account associated with GUIDE and remove the app from their phones. Participants in the waitlist group will get the opportunity access to the GUIDE App at this meeting if they are interested.

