**The following documents are currently attached to this item:**

*There are no documents attached for this item.*

**If there is subject compensation, provide the schedule for compensation per study visit or session and total amount for entire participation, either as text or separate document**

All participants will receive \$100 for completing the trial, in two disbursements: \$50 after completion of the baseline assessment, and \$50 after completion of the post-treatment assessment. Payments will be sent via Greenphire ClinCard®, from an account managed by the research team. Participants randomly assigned to the immediate group with incentives will have the opportunity to earn an additional \$100 from the GUIDE team. Payments will be remitted on a weekly basis in increasing increments according to the following payment schedule: \$10 for week one, \$20 for week two, \$30 for week three, and \$40 for week four. In order to qualify for each weekly disbursement, participants in the immediate group with incentives must complete specific tasks each week, including: completing at least three lessons, posting at least three times, commenting at least three times, completing three How I Am Feeling exercises, and liking three peer posts. Compensation will be provided in Amazon gift cards emailed directly to the participant from the GUIDE team.

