
compensation for their participation. If they complete certain weekly tasks, they will be emailed Amazon gift cards by the GUIDE team. These tasks include completing at least three lessons, posting at least three times, commenting at least three times, liking three peer posts, and completing three How I Am Feeling exercises. When the four-week trial period is over, participants will receive an email from REDCap with a link to their post-trial assessment survey. The survey will include the same measures from the baseline assessment, but without demographic questions. We will also include a question about whether they are still employed, to report on retention. The survey will include four additional measures that assess the feasibility and usability of the app for participants in the immediate and immediate with incentives groups, including: the System Usability Scale (SUS), the Acceptability of Intervention Measure (AIM), the Intervention Appropriateness Measure (IAM), and the Feasibility of Intervention Measure (FIM). When the trial is over, participants who have not yet scheduled their post-trial meeting will receive an email reminder from the research team and a link to a calendar management software, such as Microsoft Bookings. The post-trial meeting will be brief, about 15-30 minutes, and held over Zoom. It will not be recorded. During the post-trial meeting, participants who have not yet completed their post-trial assessment will be given time to do so. They will also get the opportunity to give feedback about the GUIDE App and the trial. Participants in the immediate and immediate with incentives groups will be told that they may delete their GUIDE account and remove the app from their phones; while participants in the waitlist group will get the opportunity access to the GUIDE App at this meeting if they are interested. Participant feedback and suggestions about the app will be consolidated and discussed with the GUIDE team.

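### The adverse event checklist is given only at the post-trial meeting, not in the paid post-trial survey, so participants who skip the meeting or withdraw give no checklist data

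*Combined protocol and SAP*

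**What the plan says.** The protocol mentions the checklist in two places, both tied to the closing Zoom meeting.

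- Study Instruments: "During the post-trial meeting, we will review a brief Adverse Event Checklist with participants". It adds: "This checklist contains four questions and is attached to this application".
- Administration of Surveys and/or Process, in the account of that meeting: "The research team will also review a brief Adverse Event Checklist with these participants and record their responses".

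The Procedures section describes the same meeting ("The post-trial meeting will be brief, about 15-30 minutes, and held over Zoom"). It covers unfinished surveys, feedback, account deletion and waitlist access, but not the checklist.

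On payment, Administration of Surveys and/or Process gives $50 "in compensation for completing this survey, remitted through a Greenphire ClinCard". Subject compensation places the second $50 "after completion of the post-treatment assessment". No payment is named for attending the meeting.

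On survey content, Procedures says: "The survey will include the same measures from the baseline assessment, but without demographic questions". It adds an employment question and, in the two app arms, four feasibility and usability measures. Group Modifications agrees on those four. No adverse event item is listed.

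**The concern.** Systematic adverse event collection depends on one encounter that is separate from the paid task. The survey link is emailed when the four weeks end, so the survey can be finished, and the payment earned, without attending. Withdrawal is allowed at any time, and the visible text describes no checklist contact for someone who withdraws. Those who do not book the meeting are sent a scheduling reminder, not the checklist.

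The main worry is informative absence. A participant who stopped because the content or the group chat was upsetting may be less willing to join a one-to-one call. The section on potential risks itself lists discomfort in the post-trial interview as a possible risk. If absence is related to harm, the rate among attenders is too low. If attendance differs between arms, the comparison of arms is affected as well, in a direction the documents do not let us predict.

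The omission from Procedures adds a practical risk: staff working from that section could run the meeting without the checklist.

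**Working it through.** **1. Who has a checklist record if the plan is followed as written**

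| Participant | Paid survey | Meeting | Checklist record |
|---|---|---|---|
| Completes both | yes | yes | yes (if staff follow Study Instruments; Procedures omits it) |
| Completes survey, skips meeting | yes | no | none |
| Attends meeting, survey unfinished | time given in the meeting | yes | yes |
| Withdraws, or does neither | no | no | none |

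The second and fourth rows are the gap.

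**2. Other safety information**

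- In-app flagging (Procedures; Potential Study Risks): moderators pass suicide-related content to the research team within 24 hours. It covers only what is disclosed in the app and cannot reach the waitlist arm during the trial.
- PHQ-8 and GAD-7 are repeated in the post-trial survey. They exist for a survey completer who skips the meeting. The outcome section lists them as measures of the primary proximal outcome, and no section designates them as safety measures.
- The Data and Safety Monitoring statement says the principal investigator monitors safety throughout, but gives no procedure for collecting events. The Analysis Plan does not mention adverse events.

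**3. Possible size**

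The plan has no figure of its own to reproduce: it states no expected attrition, attendance or event rate. The planned size is 50 per arm, so 100 app users. Everything else here is assumed.

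Let R be the true event rate, d the share absent, and k the risk in absentees relative to attenders.

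- Rate recorded among attenders: a = R / ((1 − d) + d × k)
- Share of events missed: m = d × k × a / R

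With R = 10% and d = 20%:

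- k = 1: a = 0.10 / (0.8 + 0.2) = 10.0%; m = 20%
- k = 2: a = 0.10 / (0.8 + 0.4) = 8.3%; m = 0.4 × 0.0833 / 0.10 = 33%
- k = 3: a = 0.10 / (0.8 + 0.6) = 7.1%; m = 0.6 × 0.0714 / 0.10 = 43%

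Recorded rate, with the share of events missed in brackets, over a range of absence:

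| Absent | k = 1 | k = 2 | k = 3 |
|---|---|---|---|
| 10% | 10.0% (10%) | 9.1% (18%) | 8.3% (25%) |
| 20% | 10.0% (20%) | 8.3% (33%) | 7.1% (43%) |
| 30% | 10.0% (30%) | 7.7% (46%) | 6.25% (56%) |

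These rates use attenders as the denominator. If absentees were silently counted as event-free, the rates at 20% absence would be 0.8 times as large: 8.0%, 6.7% and 5.7%.

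**4. Loss of precision alone**

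With zero events among n people assessed, the exact one-sided 95% upper limit is 1 − 0.05^(1/n). For all 100 app users it is 2.95%; with 20% absent (n = 80) it is 3.68%. That loss is modest. The larger problem is absence related to harm.

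**The case against.** The strongest reply is that the trial is not blind to harm and that the meeting is not easy to miss.

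- A reader might infer that people who skip the meeting or quit contribute no safety data at all. The documents do not support that. App users are covered by suicide flagging with follow-up by the principal investigator, and survey completers give PHQ-8 and GAD-7 scores. This objection stands, and the point is limited to checklist data.
- A reader might call the meeting unpaid. That is an inference. Subject compensation also presents the $100 as payment for completing the trial, and at the meeting "participants who have not yet completed their post-trial assessment will be given time to do so", so some will do the paid task there. What the text supports is that no separate payment is named for the meeting.
- Attendance has safeguards. Procedures has the meeting booked during intake; the survey administration section has a scheduling email sent after intake. Both send reminders to those not booked. It would be tempting to say that waitlist members have a reason to attend (app access) and app users have none. However, the meeting is also where app users give feedback and learn about account deletion, and no figure supports a difference.
- A reader might infer that the coordinator who trains app users also asks the checklist questions knowing the arm. The documents assign the coordinator to intake and give the checklist to the research team. Participants know their own arm in any case, so self-report would not remove that source of bias.
- The checklist, consent forms and modification documents are attachments that are not shown. The absence of withdrawal contact means only that none is described in the visible text.
- Survey items will not recover someone who answers nothing, and an interviewer can probe in a way a form cannot. Both are true, which is why the meeting should stay.

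None of this supplies a checklist record for survey completers who miss the meeting, or for those who withdraw.

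**Conclusion.** The concern holds in limited form. As the text stands, checklist data come only from people who attend the post-trial meeting, and the section that sets out that meeting in Procedures leaves the checklist out. The effect cannot be estimated from the documents. Under the assumptions of 20% absence and a 10% true rate, the recorded rate ranges from 10% (absence unrelated to harm) through 8.3% to 7.1% (two and three times the risk in absentees). If attendance is near complete, little is lost.

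It would go too far to say that the plan's judgement of minimal to no risk would be falsely confirmed. That is a prospective statement, and the Analysis Plan does not set out to test it with checklist data. The change is still worth making, because it is cheap and closes most of a gap that cannot be repaired after the data are in.

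**What to change.** - Add the same four questions to the post-trial REDCap survey in all three arms, so that they are part of the paid step.
- Send them automatically, as a short form, to anyone who withdraws or does not book the meeting.
- Keep the meeting for following up positive answers, and state who reviews them.
- Add the checklist to the description of the meeting in Procedures, and replace the loose reference to these participants in the survey administration section with all arms.
- Add to the Analysis Plan a descriptive table of adverse events by arm, with the number assessed as denominator and not assessed shown separately from none.

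The cost is four items on a survey of 100 questions (waitlist) or 123 (app arms), about a minute of participant time, one REDCap trigger, one table, and staff time to follow up positive self-reports. People who answer neither the survey nor the trigger will remain missing. The table should count them, not treat them as event-free.
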